2.2.2 Analysis of Categorical Data

For categorial variables (e.g. gender, etc.), results will be summarized with subject counts and percentages/rates, and where applicable, with exact 95% Clopper-Pearson² confidence intervals. The p-values will be based on either Pearson's Chi-square test or Fisher's exact test by checking the expected frequency for each cell in the maximum contingency table against Cochran's rule³ (i.e. if the expected frequencies for all cells are ≥ 5 , then Pearson's Chi-square test will be used, otherwise Fisher's exact test will be used).

2.2.3 Survival Analyses

Survival analysis will be conducted to analyze time-to-event variables (e.g., time to all cause of death) in the following three scenarios:

- Subject with event of interest, the time to event will be calculated from the date of randomization /permanent implant to the date of event occurred.
- Subjects without events will be censored at the date of withdrawal, or

Statistical Analysis Plan

- Subjects without events with the date of the completion of their follow-ups, or at their last known event-free time point.

Survival curves will be constructed using Kaplan-Meier⁴ estimates. Summary tables for events of interest will include event (failure) rates, Greenwood standard error, and confidence interval for the event rates.

2.2.4 Regression

2.2.4.1 Logistic regression model

Unconditional logistic regression may be used by adjusting baseline characteristic for binary variables.

2.2.4.2 Mixed effects model

For repeated measured variables, such as responder rate, patient report outcomes (PROs) at each visit, mixed effects models may be used to conduct exploratory analyses to evaluate the difference between SCS and CMM. Data can be analyzed using proc mixed for continuous variables or proc glimmix for binary variables from SAS®. Models will be compared and selected using likelihood ratio test, AIC or BIC.

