6.6.4 Crossover

Crossover prior to the study primary endpoint is not allowed. To ensure valid analysis of all endpoints, investigators and coordinators must make concerted efforts to prevent crossover from CMM to SCS prior to completing the 6-month visit. If a subject is unwilling to complete the assigned treatment, they should be withdrawn. Upon completion of the 6-month primary endpoint visit, a subject is allowed to crossover to the other arm. The permanent implant must occur prior to the [REDACTED] follow up visit.

Clinical Investigation Plan

Subjects crossing over to the SCS arm will follow the trial and permanent SCS procedures as part of standard of care. Upon receiving a permanent implant, subjects will continue to participate in the study according to Section 6.6. The follow-up timeline will not be reset; the subject will continue with the follow-up schedule. Subjects are not allowed to crossover more than once.

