2.0 ANALYSIS CONSIDERATIONS

2.1 Analysis Populations

The analysis populations include:

1. Intention-to-Treat (ITT) Population: includes all randomized subjects. Subjects will be analyzed according to the treatment group they are randomized to. The ITT population will be used as the primary analysis population for the primary endpoint.
2. Modified Intention-to-Treat (mITT) Population: includes all randomized subjects except for those who are randomized to the SCS group who fail the trial period, do not receive a permanent system implant. Subjects will be analyzed according to the treatment group they are randomized to.
3. Per-Treatment Evaluable (PTE) Population: includes all subjects in the mITT population who either receive permanent implant or receive CMM. Subjects will be analyzed according to the actual treatment received. The PTE population will be used as the primary analysis population for the study except the primary endpoint analysis.

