2.2 Statistical Methods

2.2.1 Analysis of Continuous Data

For continuous variables (e.g., age, etc.), results will be summarized as number of observations, means, and standard deviations, and where applicable, with quartiles, minimums, maximums, and 95% confidence intervals for the means. Difference between two groups, when specified, will be summarized with difference of the two means, and the 95% confidence interval of the differences. The p-values will be calculated based on either two-sample t-test or Wilcoxon rank sum test as appropriate.

Cumulative distribution function (CDF) may be used in displaying a continuous plot of the percent change from baseline on the horizontal axis and the cumulative percent of patients experiencing up to that change on the vertical axis. Kolmogorov-Smirnov test may be used to test whether two empirical distributions are different using proc npar1way in SAS®¹.

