2.4 Sample Size/Power Calculations

The study was designed to enroll approximately 200 subjects in Phase I and up to 70 subjects in Phase II. The following assumptions are used in the power calculation for the primary endpoint:

- Assumed response rate of 45% for the SCS group and 20% for the CMM group
- 3:2 (SCS:CMM) randomization ratio
- 25% attrition rate to primary endpoint (6 months) follow-up in both groups
- Two-sided alpha of 0.05
- Z-test with unequal variance

Based on the assumptions above, there is at least 90% power to evaluate the primary endpoint with the Phase I cohort.

The minimum detectable differences for secondary endpoints using phase I PTE cohort (assume approximately 80 SCS and 60 CMM) with 80% power are shown in Table 1 below.

Table 1: Minimum Detectable Differences (MID) for Secondary Endpoints

Secondary Endpoints	MID (standard deviation for each group)
#1: Composite Responder	23%
#2: Relative NRS Change in %	16.9(35)
#3: ODI Change	7.2 (15)
#4: PCS Responder	21%
#5: PGIC (%)	23%
#6: Relative Pain Interference Change in %	7.2 (15)
#7: Relative Physical Function Change in %	12.0 (25)

The sample size re-estimation will be based on the interim analysis (IA) population (Adaptive Design Plan CL1014964). The unblinded independent statistician will perform the sample size re-estimation for 4 endpoints (1 primary and secondary endpoints #1, #2, and #3) and generate a recommendation if more subjects are needed to meet the statistical significance of each endpoint.

The power calculation was performed using PASS 15 (NCSS LLC).⁵

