2.11 Multiplicity Issues

To control for type I error inflation, the test of secondary endpoints will be performed in a hierarchical order at two-sided 5% significance level:

1. Secondary endpoint #1
2. Secondary endpoint #2
3. Secondary endpoint #3
4. Secondary endpoint #4
5. Secondary endpoint #5
6. Secondary endpoint #6
7. Secondary endpoint #7

The secondary endpoints will be tested only if the superiority in the SCS group is demonstrated in the primary endpoint. If hypothesis testing for superiority of secondary endpoint #1 fails, no hypothesis testing for the rest of secondary endpoints, etc.

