2.12 Sensitivity Analysis

Sensitivity analysis will be conducted for the primary endpoint, as specified in Section 2.3.1.2.

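### The gatekept continuous secondaries (#2, #3, #6, #7) have only a two-sample test at month 6 and no missing-data method, while collected month-1 and month-3 scores go unused

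*SAP*

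**What the plan says.** SAP 2.3.2 defines #2 (relative NRS change), #3 (ODI change), #6 (relative PROMIS pain interference change) and #7 (relative PROMIS physical function change) by formulas that need a baseline and a month-6 score. It names no test for them. The general rule in SAP 2.2.1 is: "The p-values will be calculated based on either two-sample t-test or Wilcoxon rank sum test as appropriate".

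These endpoints are confirmatory. SAP 2.11 states that "the test of secondary endpoints will be performed in a hierarchical order at two-sided 5% significance level", after success on the primary, and a failure ends the sequence. The analysis set comes from SAP 2.1: "The PTE population will be used as the primary analysis population for the study except the primary endpoint analysis".

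On missing data, SAP 2.9 describes multiple imputation for the primary endpoint only, and SAP 2.12 adds: "Sensitivity analysis will be conducted for the primary endpoint, as specified in Section 2.3.1.2". The visible text gives no rule for any secondary. The requirement to complete the month-6 visit (SAP 2.3.1.1) is written for the primary.

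Months 1 and 3 are required visits (SAP 1.3). NRS, ODI and PROMIS-29 are on the list of data for each visit (protocol 6.6.1). SAP 2.2.4.2 names PROC MIXED for repeated outcomes, but says only that "mixed effects models may be used to conduct exploratory analyses to evaluate the difference between SCS and CMM".

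The power section assumes a "25% attrition rate to primary endpoint (6 months) follow-up in both groups". Before month 6, protocol 6.6.4 directs: "If a subject is unwilling to complete the assigned treatment, they should be withdrawn". Protocol 5.6 lists explant as a reason for discontinuation and requires no outcome data after withdrawal.

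**The concern.** A two-sample test on a month-6 change score can use only subjects who have one. It estimates the arm difference in the analysis set without bias only if, within each arm, those who stay represent those who leave, or if the distortion is the same in both arms and cancels.

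Neither can be presumed here. Subjects and sites know the assignment (SAP 1.6), the two treatments are very different in kind, and unwillingness to continue leads to withdrawal. If CMM subjects without relief leave, the remaining CMM group looks too good and the difference shrinks. If SCS subjects without relief leave, the difference grows.

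A shrunken difference can stop the sequence at #2 or #3 and so block everything below. An inflated one raises the chance of a false claim. Endpoints #2 and #3 also feed the sample size re-estimation (SAP 2.4).

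The plan already treats early scores as informative: SAP 2.9 lists the 3-month NRS as a candidate predictor for imputing the primary. It does not carry this over to the secondaries.

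**Working it through.** **1. Reproduce Table 1.** SAP 2.4 uses the "phase I PTE cohort (assume approximately 80 SCS and 60 CMM) with 80% power", two-sided alpha 0.05. For #2 (SD 35):

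- SE = 35 × √(1/80 + 1/60) = 35 × 0.1708 = 5.98.
- Normal approximation: (1.960 + 0.842) × 5.98 = 16.75. With the noncentral t on 138 df: 16.86. Table 1 gives 16.9.
- By the same t calculation, #3 and #6 (SD 15) give 7.23 against 7.2, and #7 (SD 25) gives 12.05 against 12.0.

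The table reproduces, so its figures are minimum detectable differences for two-sample tests on 80 and 60 observed subjects.

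**2. Bias of the completers' mean.** Suppose leaving in one arm depends on the standardised early score z, with odds ratio OR per SD worse relief and attrition of 25%. Let rho be the correlation between the early and the month-6 score. Then

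bias = rho × SD × E[z | retained].

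OR and rho are not in the documents and are assumed. With rho 0.6, E[z | retained] is 0.098, 0.159 and 0.228 for OR 1.5, 2 and 3. For #2:

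- OR 1.5: 0.6 × 35 × 0.098 = 2.1 points, 12% of 16.9
- OR 2: 0.6 × 35 × 0.159 = 3.3 points, 20%
- OR 3: 0.6 × 35 × 0.228 = 4.8 points, 28%

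**3. Simulation with two early visits.** Settings: 107 SCS and 80 CMM, each losing 25% to reach about 80 and 60 (80/0.75 = 106.7; 60/0.75 = 80); correlations 0.6 (months 1 and 3), 0.7 (3 and 6) and 0.5 (1 and 6); half the exits after month 1 and half after month 3; dependence in one arm only. The percentages come from unrounded biases.

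| OR per SD | Bias, points | % of 16.9 | Power if CMM-dependent | Null rejection if SCS-dependent |
|---|---|---|---|---|
| 1.5 | 2.3 | 13% | 69% | 7% |
| 2 | 3.7 | 22% | 60% | 10% |
| 3 | 5.3 | 32% | 51% | 14% |

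Hand check: power ≈ Φ((16.9 − bias)/5.98 − 1.96) gives 69%, 60% and 49%. Null rejection ≈ Φ(bias/5.98 − 1.96) + Φ(−bias/5.98 − 1.96) gives 7%, 9% and 14%.

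**4. The same data with months 1 and 3 used.** A likelihood estimate, equivalent to an unstructured mixed model, has bias within 0.2 point in these scenarios. When exit is unrelated to outcome, both methods are unbiased; the standard error is 5.6 against 5.9, and power 85% against 81%.

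**5. Where the effect is smaller.**

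- Same exit rate and dependence in both arms: zero bias.
- SCS exit after month 1 or 3 of only 5% to 10% (assumed), OR 1.5 to 3: 0.4 to 2.1 points, 2% to 13% of 16.9, and null rejection 5.0% to 6.5%.
- #3, #6 and #7, if early pain relief correlates only 0.3 with the outcome: half the step 2 percentages, about 6% to 14% of the minimum detectable difference.
- Half the leavers gone before month 1: the mixed model itself keeps a bias of 5% to 13%.

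**The case against.** The strongest reply is that the size is assumed. No exit odds ratio or between-visit correlation is in the documents. Over a wider grid (attrition 10% to 25%, from weak dependence to exit below a sharp relief threshold) the bias runs from about 2% to 70% of the minimum detectable difference. This stands, and the figures are illustrations.

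The SCS input is also partly constructed. With 200 subjects at 3:2 there are 120 SCS and 80 CMM, so 80 evaluable SCS subjects is 67%, not 75%. Some of that loss is trial failures without an implant, who lie outside the PTE set; a mixed model does not bring them back. Exit among implanted subjects may be well below 25%, which weakens the false-positive argument in particular. This also stands.

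There are mitigations. Sites should attempt a final visit with patient-reported outcomes when consent is withdrawn (protocol 5.6), and remote or mailed questionnaires are allowed (protocol 6.6.1, 6.6.2). These may reduce the missing data but do not say how to analyse what remains.

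The protocol's method for continuous secondaries is redacted (8.2.2), and the Adaptive Design Plan was not available. The criticism therefore rests on the SAP, to which the protocol refers for details. Finally, trial success depends on the primary alone (SAP 2.7), which limits the consequence but does not remove it for claims made under alpha control.

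**Conclusion.** The point holds as a gap in the confirmatory plan. Four alpha-controlled endpoints have a two-sample rule, no missing-data method and no sensitivity analysis, while a better-suited model and the data for it are already in the trial.

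For #2, under the stated assumptions, the bias is about 2 to 5 points (13% to 32% of 16.9). Power falls to between 69% and 51% if CMM exit is dependent; null rejection is about 7% to 14% if SCS exit is dependent. It is near zero if both arms behave alike.

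A reader might infer more than the documents support:

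- That the SAP prescribes completers only for these endpoints. It does not say so; the change formulas and the test imply it.
- That a fixed share of the planned effect is lost on all four. Table 1 gives minimum detectable differences, not planned effects. Only #2 was simulated, and the effect on the others may be smaller.
- That early scores exist for everyone who leaves. They exist only for those who stay to month 1 or month 3.

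**What to change.** **Confirmatory test.** In SAP 2.3.2, with a matching change to 2.2.4.2, make the month-6 arm contrast from a repeated-measures mixed model the test for #2, #3, #6 and #7. Model change at months 1, 3 and 6 with arm, visit, arm-by-visit, baseline and baseline-by-visit, and an unstructured covariance. Use visits to month 6 only, so that crossover does not enter. Keep the two-sample comparison as supportive.

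**Binary secondaries.** In SAP 2.12, extend the multiple imputation of 2.9 to #1, #4 and #5 as a sensitivity analysis.

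**Sample size increase.** The interim falls when 70% of Phase I reach month 6 (SAP 2.5), so other subjects will then have only month-1 or month-3 scores. Assign each subject to one CHW stage in advance, so that nobody contributes to both, and align this with the Adaptive Design Plan.

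**Cost.** SAP wording and programming before unblinding; no new visits, data or subjects. The model assumes missing at random given the observed scores, which is weaker than what the completers' test needs. It also assumes approximate normality, for a bounded percentage change in #2, and gives up the Wilcoxon option as the lead test. Subjects who leave before month 1 and non-implanted SCS subjects outside the PTE set are still not recovered.

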2.3 Endpoint Analysis

2.3.1 Primary Endpoint

The primary effectiveness endpoint is the difference in response rates between groups at 6 months. A subject is considered a responder for the primary endpoint if the following criterion is met:

Improvement in pain, defined as a $\geq 50\%$ decrease on NRS.

2.3.1.1 The Hypothesis Test:

$$H_0: P_{SCS} = P_{CMM}$$

$$H_a: P_{SCS} \neq P_{CMM}$$

P_{SCS} and P_{CMM} denote the response rate at 6 months for SCS and CMM groups, respectively.

The ITT population defined in Section 2.1 will be used as the primary analysis. Trial failures (defined as having $< 50\%$ decrease in pain on the NRS from baseline to the end of the trialing, and who withdrew from the study per CIP), will be counted as non-responders in this analysis. All other subjects must complete their 6-month visit and have available primary endpoint data to be included in the primary analysis.

The response rates between the two groups will be compared using a two-sided Z-test with unpooled variance at the significance level of 0.05.

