There are several factors (psychological, economic, comorbidities) that impact the course of the condition and an individual's response to treatment. It is likely that treatment success depends not only on reducing pain intensity, but also on improving functional capacity. In addition to the recognized psychological factors that impact the course of pain and response to treatment (e.g., pain catastrophizing, depression, anxiety), other factors such as smoking history, obesity, diabetes and financial/legal status also influence treatment outcomes.

The widely accepted treatment algorithm for low back pain in an acute state begins with conservative care consisting of physiotherapy and medication optimization. Low back pain persisting for more than three months is considered chronic. Patients with CLBP are likely to be offered non-operative interventions such as anesthetic or steroid injections, radiofrequency ablation, and opioid therapy. Those with a clear anatomic pain generator may be offered surgery. Even with successful surgery at the correct anatomical level, there is inconsistent clinical effectiveness, and significant pain can persist from the original cause or from the post-surgical healing process (5-7). This phenomenon is commonly referred to as Failed Back Surgery Syndrome (FBSS).

Clinical Investigation Plan

Currently, SCS is used in patients who have failed other treatment options for CLBP and have reached the end of the treatment continuum. Unfortunately, this is despite evidence that a longer time to treatment predicts lower chance of therapeutic success, and poor outcomes of surgery in the absence of spinal instability (8).

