2.9 Handling of Missing Data

As discussed in Section 2.3.1.2, for a sensitivity analysis of the primary endpoint, subjects with missing primary endpoint outcomes will have their outcomes imputed with multiple imputation (MI). PROC MI in SAS will be used to multiply impute missing outcomes. Multivariate imputations by fully conditional specification (FCS) methods with 20 burn-in interactions before each imputation, and the number of imputations equal to the percentage of missing data, and a seed of 8684915 will be used for analysis. If FCS methods fail to converge, other methods will be explored for the MI model.

The model may include, but not be limited to, the following predictors:

- Randomization group
- Age
- Sex at birth
- Lower back NRS at baseline and 3 months
- Duration of pain

If the model does not converge with this list of predictors, predictors will be removed from the model as needed to ensure convergence.

Once multiply imputed datasets have been generated, each imputation will be analyzed with standard statistical analyses before being combined for inferential analyses using PROC MIANALYZE. Example code which may be used is included in Appendix B.

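### The primary Z-test is valid and meets its stated power, but it uses no baseline covariate; adjusting the same risk difference for baseline PCS and NRS offers a modest gain that depends on assumed prognostic strength

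*SAP*

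**What the plan says.** SAP 2.3.1.1 defines the primary analysis, in which the two response rates are "compared using a two-sided Z-test with unpooled variance at the significance level of 0.05". SAP 2.3.1.2 repeats the same test in the mITT and PTE populations. The multiple-imputation sensitivity analysis uses covariates to fill in missing outcomes and does not prescribe an adjusted comparison. The power calculation in SAP 2.4 assumes the same unadjusted test.

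The only adjustment text for binary outcomes is SAP 2.2.4.1: "Unconditional logistic regression may be used by adjusting baseline characteristic for binary variables". It is optional and names neither an endpoint nor a covariate.

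Protocol 1.1.1 refers to "recognized psychological factors that impact the course of pain and response to treatment", giving catastrophizing, depression and anxiety as examples. It adds that "a longer time to treatment predicts lower chance of therapeutic success". Protocol 6.2.2 lists low-back NRS, PCS, PROMIS-29 and ODI among the baseline measures. SAP 2.9 offers age, sex, pain duration and "Lower back NRS at baseline and 3 months" as possible imputation predictors; PCS is not on that list.

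**The concern.** The Protocol treats some patient characteristics as related to response, and the trial measures several of them before treatment, yet the primary estimate ignores them. Any outcome variance that they explain stays in the standard error of the difference. With about 60 evaluable CMM subjects, a visible chance imbalance in PCS is likely to be raised when results are read. No pre-specified adjusted estimate would then exist to answer it.

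The optional logistic regression does not fill this gap. Its covariates would be chosen later, in a trial where subjects and sites know the assignment. Its usual output, a conditional odds ratio, is also not the difference in response rates that the plan names as its endpoint.

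**Working it through.** **Inputs.** From SAP 2.4: "Assumed response rate of 45% for the SCS group and 20% for the CMM group"; "Two-sided alpha of 0.05"; 3:2 allocation; 25% attrition in both groups; 200 subjects in Phase I. From SAP 2.5: one interim analysis at 70% of Phase I. Not in the documents: how strongly baseline covariates predict a 50% fall in NRS. That is an assumption throughout.

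**The plan's own power.** Evaluable: 200 × 0.75 = 150, that is 90 SCS and 60 CMM.

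SE = √(0.45×0.55/90 + 0.20×0.80/60) = √(0.00275 + 0.00267) = 0.0736.

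Power = Φ(0.25/0.0736 − 1.96) = Φ(1.437) = 92.5%. Exact enumeration of the same test gives 91.5%. For 90% power the unpooled test needs 83 + 55 = 138 evaluable, or 138/0.75 = 184 randomized. The stated figure is met.

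**Effect of adjustment, by formula.** If covariates remove a fraction R² of the variance, SE becomes 0.0736 × √(1 − R²), and the equivalent randomized number is 200/(1 − R²).

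| R² (assumed) | SE | 95% CI half-width (points) | Power | Equivalent randomized |
|---|---|---|---|---|
| 0% | 0.0736 | 14.4 | 92.5% | 200 |
| 2% | 0.0729 | 14.3 | 92.9% | 204 |
| 5% | 0.0717 | 14.1 | 93.6% | 211 |
| 10% | 0.0698 | 13.7 | 94.7% | 222 |
| 11% | 0.0694 | 13.6 | 95.0% | 225 |

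**Effect of adjustment, by simulation.** Setting: 90 versus 60 subjects, one normal covariate with the same slope in both arms, standardized risk difference from a logistic model, influence-function SE, 4,000 trials per setting.

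| Log-odds slope per SD | Variance change | Power at 45% vs 20%, unadjusted → adjusted |
|---|---|---|
| 0 | +0.8% | 91.7% → 91.4% |
| 0.3 | −1.2% | 90.9% → 91.4% |
| 0.5 | −4.3% | 91.4% → 92.3% |
| 0.8 | −8.9% | 92.2% → 94.3% |
| 1.2 | −18.3% | 91.8% → 95.8% |

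Under the null, rejection was 5.1-5.7% unadjusted and 5.2-5.8% adjusted.

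Repeat runs at 90/60 gave a variance cut of 2-4% at slope 0.5 and 5-11% at slope 0.8. They gave about zero when the covariates acted only in the SCS arm, and a 1-3% loss when they were uninformative. With four covariates, the cut at slope 0.5 was only 1-2%, which favours a short list.

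**Second stage under sample size re-estimation.** After the interim, 30% of Phase I remains: 60 randomized × 0.75 = 45 evaluable, or 27/18. With all 70 Phase II subjects it is 130 × 0.75 ≈ 97, or about 58/39.

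| Second stage | Model | Two-sided type I error, adjusted | Unadjusted |
|---|---|---|---|
| 27/18 | four covariates | 6.6-7.8% | 5.0-6.1% |
| 58/39 | four covariates | 6.3-6.6% | 5.3-5.5% |
| 27/18 | one or two covariates | 4.4-6.0% | – |

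At 27/18 the four-covariate model also showed no variance gain and up to 2.5% non-convergence. A long list carried into stage-wise statistics is therefore not safe.

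**The case against.** The strongest reply is that nothing is broken. The Z-test estimates the stated endpoint, matches the power calculation and reaches its target. Chance imbalance does not bias it, because the standard error and alpha already allow for imbalance. All of that stands. A reader might infer that the primary test is wrong, biased or underpowered; the documents support none of these.

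The benefit is also uncertain. Entry requires NRS of at least 6, so baseline NRS spans only 6 to 10, and the outcome is already a percentage of baseline. Failed psychological evaluation, untreated mental illness and Waddell's signs are exclusions, which narrows the psychological range. Strong prediction, such as the slope of 1.2 above, is therefore doubtful, and I do not rest the point on it.

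Two further readings go too far. The time-to-treatment sentence follows a remark about SCS being used late, so it concerns delay before SCS and says nothing about prognosis under CMM; a covariate acting in the SCS arm alone brought no gain. SAP 2.9 does not show that the plan already accepts these predictors: its list is permissive, omits PCS and includes the post-randomization 3-month NRS.

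The reply also holds that naming covariates for a supportive adjusted analysis would be enough. That would supply a pre-specified adjusted result, but it would leave the precision gain out of the primary estimate. The warning about the small second stage stands in full and shapes the fix.

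**Conclusion.** The point holds as an efficiency and pre-specification improvement. At the plan's own 45% versus 20%, adjustment for a short covariate list would cut variance by roughly 2-11%. That is worth about 1-3 power points (0.5 to 2.5 by the formula, 0.9 to 2.1 in the tabulated simulation at slopes 0.5 and 0.8). This assumes a combined log-odds slope of about 0.5 to 0.8 per SD, the same in both arms. The gain is nil if prediction is confined to the SCS arm, and there is a loss of about 1-3% if the covariates predict nothing. The documents cannot settle which case applies.

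The case for acting is that the data are already collected, the estimand and alpha do not change, and sponsor statisticians have no access to outcomes by arm before the primary analysis (SAP 1.6), so the list can be fixed credibly beforehand. How site enters the analysis is a separate question.

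**What to change.** In SAP 2.3.1.1:

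- Estimate P_SCS − P_CMM as a standardized risk difference: fit a logistic model with arm, baseline PCS total and baseline low-back NRS, average the predicted risks under each arm over all analysed subjects, and take the difference. Test at two-sided 0.05 with a robust, small-sample-corrected standard error.
- Restrict covariates to pre-randomization values, which excludes the 3-month NRS.
- State a simple rule for missing baseline values, for example the mean over all randomized subjects regardless of arm.
- Name the unadjusted Z-test as the fallback if the model does not converge, and report it in any case as a supportive analysis.
- If the sample size is increased, use the unadjusted stage-wise Z in the CHW statistic, unless simulation shows that the adjusted version holds alpha at the second-stage size.

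Cost: SAP wording, a few lines of code and a matching check of the Adaptive Design Plan, which governs re-estimation and is not among the documents. No new data are needed. The statistical price is the 1-3% precision loss if the covariates prove uninformative.
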